During the dose expansion part of this study, BMS-986158 will initially be tested in subjects with TNBC, CRPC, DHL, non-GC-DLBCL, and NMC. These cancers are rare in children. Some predictors of poor outcome were shared among all age groups, such as multiple primary tumor sites and advanced stage disease. Because patient numbers are low, there are no randomized trials comparing different relapse regimens. These results provide rationale for development of alternative treatment approaches focusing on targeted therapy to circumvent chemotherapy-resistant disease by providing alternative therapeutic targets across different ages.

Current experience with BMS-986158 did not identify drug-related adverse events (AEs) that warrant exclusion of adolescent subjects from this study. Thus, the balance of benefit to risk may be favorable in adolescent subjects with advanced cancers and poor treatment options. Therefore, adolescent subjects with NMC will be eligible to participate in this study. Additional indications will be allowed at the discretion of the Sponsor if the tumor contains similar genetic abnormalities sensitive to regulation by the BET family proteins.

This SAP supersedes the statistical considerations identified in the protocol; where considerations are substantially different, they will be identified as such in this document. In the event that the protocol has amendment(s) that do not have an impact on the statistical analysis methodology, this SAP will not require an amendment. [REDACTED]

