Once the safety and tolerability profile is established at the selected dose of BMS-986158 alone during the dose evaluation phase, enrollment in the expansion phase will initiate at this dose level to assess a preliminary efficacy signal, and to obtain additional data, such as [REDACTED] safety information across the selected tumors.

Enrollment in the Part 2 expansion will start in the initial BMS-986158 monotherapy cohorts. Although a 2-stage (Fleming) design will be used to guide assessment of preliminary anti-tumor activity in each of the monotherapy cohorts, up to 9 subjects may be enrolled in each of the initial cohorts to better characterize the PK, safety [REDACTED] profiles. The decision to continue or discontinue enrollment in one or more cohorts or discontinue treatment in existing cohorts will be made by the Sponsor/Medical Monitor based on a comprehensive assessment of the accruing on-treatment evidence.

Clinical safety monitoring of subjects during dose expansion phase will continue throughout the study. If at a selected BMS-986158 dose level, the combined incidence exceeds 33% for study drug related toxicity requiring treatment discontinuation, further enrollment to that dose level may be interrupted and a decision to continue dosing will be based on discussions of the observed aggregate (acute and chronic) toxicities between the investigator(s) and the Sponsor, if needed.

Table 2.2-1 shows the planned number of subjects per tumor type and setting (Part 2 Initial monotherapy) in the expansion phase.

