### **5.2 Dose-expansion Cohort**

The purpose of cohort expansion is to gather additional safety, tolerability, preliminary efficacy, PK, [REDACTED] information regarding BMS-986158 alone. However, the sample size is strictly based on efficacy, specifically based on the target ORR relative to historic response rate.

During this part of the study, the efficacy signal assessment in each tumor cohort in monotherapy regimens will be guided by a Fleming 2-stage design. The Stage 1 and total (Stages 1 and 2) sample size for each cohort is calculated based on assumptions of true (target) and historic ORR for each tumor type in the studied population. Using a 2-stage design provides an option to stop early for futility, as well as an early signal of preliminary strong antitumor activity. Approximately 5 to 9 subjects will be treated in each of the 5 parallel cohorts. Enrollment may continue during the initial

Stage 1 efficacy evaluation (while the planned number of participants for Stage 1 are followed for evaluable tumor assessments) to ensure that sufficient subjects are response evaluable in case of early drop outs and to account for design parameters changes (eg, historical rate update).

The total sample size for each expansion cohort will be calculated to provide a reasonable false-positive rate (FPR < 10%) and false-negative rate (FNR < 10%) based on assumptions of true (target) and historic ORR for each indication. The assumed historic and target response rates may change over time and may need to be adjusted by the time of response data from this study are available. Enrollment may continue into stage 2 while the planned number of participants for stage 1 are followed for efficacy evaluable tumor assessments. There will be no stopping of a disease cohort for efficacy, although early planning for the next stage of clinical development may be initiated.

If one or more of the 5 subjects in a Stage 1 cohort respond to therapy, the Fleming Stage 1 futility boundary will have been exceeded and enrollment will continue in Stage 2. If 2 or fewer of 9 subjects enrolled through Stage 2 respond to therapy, the cohort will have failed to evidence the targeted ORR (Table 5.2-1).

**Table 5.2-1: Characteristics for Initial Monotherapy Expansion Cohorts Signal assessment when guided by a Two-Stage Design**

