Tumor Cohort and Group	Target ORR %	SOC ORR %	Stage 1 / Total N	Stage 1 Res Futility/ Efficacy Boundary	Stage 2 Res Futility/ Efficacy Boundary	FPR/FNR (%)
FUSION PROTEINS						
NMC	50	10	5/9	0/2	2/3	10/10
DHL	50	10	5/9	0/2	2/3	10/10
BRD AMPLIFICATIONS						
TNBC	50	10	5/9	0/2	2/3	10/10
MYC AMPLIFICATIONS						
Non-GC-DLBCL	35	10	5/9	0/2	1/2	20/20
AR AMPLIFICATIONS						
CRPC	35	10	5/9	0/2	1/2	20/20

Abbreviations: CRPC = castrate-resistant prostate cancer; DHL = double-hit lymphoma; FNR = false negative rate; FPR = false positive rate; N = number of subjects; NMC = NUT-midline carcinoma; ORR = objective response rate; RCC = renal cell carcinoma; Res = response; SOC = standard of care; TNBC = triple negative breast cancer; Non-GC-DLBCL = Non-germinal center diffuse large B-cell lymphoma;

The planned sample size consists of up to approximately 90 subjects for Part 1 and up to approximately 45 subjects for Part 2 Initial expansion for a total of up to approximately 135 subjects in the entire study (up to Part 2 Initial expansion, as clarified in the scope of this SAP document in the beginning).

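### SAP 5.2 applies one final rule (2 or fewer of 9 = failed) and one error target (<10%/<10%) to all five cohorts; its own Table 5.2-1 gives non-GC-DLBCL and CRPC a 1/2 boundary and 20/20

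*SAP*

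**What the plan says.** SAP Section 5.2 describes a Fleming two-stage design for five parallel monotherapy cohorts, with 5 subjects at Stage 1 and 9 in total.

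- **Error target, text:** both rates are to be kept under ten per cent ("FPR < 10%) and false-negative rate (FNR < 10", in per cent). The sentence is about each expansion cohort and makes no exception.
- **Stage 1, text:** one or more responders among 5 takes the cohort past the futility boundary. On early success: "There will be no stopping of a disease cohort for efficacy".
- **Final rule, text:** "If 2 or fewer of 9 subjects enrolled through Stage 2 respond to therapy, the cohort will have failed to evidence the targeted ORR". The sentence ends by citing Table 5.2-1.
- **Table 5.2-1:** NMC, DHL and TNBC have target ORR 50%, standard-of-care ORR 10%, Stage 2 boundary 2/3 and FPR/FNR 10/10. The other two rows read "Non-GC-DLBCL 35 10 5/9 0/2 1/2 20/20" and "CRPC 35 10 5/9 0/2 1/2 20/20".

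Table 8.1-2 in Protocol Section 8.1 has the same values in every row. The protocol text around it contains neither the blanket final rule nor the <10% target.

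On precedence, SAP Section 1 states: "This SAP supersedes the statistical considerations identified in the protocol; where considerations are substantially different, they will be identified as such in this document". No changed threshold is flagged for either 35%-target cohort.

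**The concern.** In the table's Stage 2 column the first number is the highest futile count and the second is the lowest count meeting the efficacy boundary. For non-GC-DLBCL and CRPC, 1/2 therefore means that 1 or fewer of 9 is futile and 2 or more meets the boundary. The sentence citing the table calls 2 of 9 a failure in every cohort, so one result has two opposite readings in two of the five cohorts.

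The error target conflicts in the same way: below 10% for both rates in the text, 20/20 in the table for these cohorts.

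The precedence clause does not settle it. It ranks the SAP over the protocol, but the conflict lies inside the SAP, between its prose and its own table. In an open-label study with ongoing data review, leaving the choice of rule until a cohort has finished at 2 of 9 would make that choice post hoc.

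**Working it through.** **Inputs (SAP Table 5.2-1, matching Protocol Table 8.1-2).** n1 = 5, n = 9, so n2 = 4. Futile at 0 of 5. Standard-of-care ORR p0 = 0.10; target p1 = 0.35 (non-GC-DLBCL, CRPC) or 0.50 (NMC, DHL, TNBC). Let X1 ~ Bin(5, p) and X2 ~ Bin(4, p) be the Stage 1 and Stage 2 responders. FPR = P(pass | p0); FNR = 1 − P(pass | p1). The table's error rates are read as upper limits.

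**Step 1: reproduce the table, 35% cohorts (pass at 2 or more of 9).**

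P(pass) = P(X1 ≥ 2) + P(X1 = 1)·P(X2 ≥ 1)

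- p = 0.10: 0.0815 + 0.3281 × 0.3439 = 0.1943, so FPR 19.4%.
- p = 0.35: 0.5716 + 0.3124 × 0.8215 = 0.8282, so FNR 17.2%.

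Both are within 20/20. Crediting 2 of 5 at Stage 1 changes nothing here, because 2 responders already pass.

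**Step 2: reproduce the table, 50% cohorts (pass at 3 or more of 9).** With no credit for reaching 2 of 5 at Stage 1, FPR is 5.1% and FNR 9.96%. With that credit they are 9.9% and 8.0%. Both fit 10/10, so the text is right for NMC, DHL and TNBC.

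**Step 3: apply the text rule to the 35% cohorts (pass at 3 or more of 9).**

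No Stage 1 credit: P(pass) = P(X1 = 1)·P(X2 ≥ 2) + P(X1 = 2)·P(X2 ≥ 1) + P(X1 ≥ 3)

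- p = 0.10: 0.3281 × 0.0523 + 0.0729 × 0.3439 + 0.0086 = 0.0508.
- p = 0.35: 0.3124 × 0.4370 + 0.3364 × 0.8215 + 0.2352 = 0.6481.

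With Stage 1 credit: P(pass) = P(X1 ≥ 2) + P(X1 = 1)·P(X2 ≥ 2)

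- p = 0.10: 0.0815 + 0.0172 = 0.0986 (rounded from unrounded terms).
- p = 0.35: 0.5716 + 0.1365 = 0.7081.

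| Rule, 35% vs 10% | FPR | FNR |
|---|---|---|
| Table: pass at ≥2 of 9 | 19.4% | 17.2% |
| Text: pass at ≥3 of 9, no Stage 1 credit | 5.1% | 35.2% |
| Text: pass at ≥3 of 9, 2 of 5 credited | 9.9% | 29.2% |

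Under the text rule the FNR exceeds both the text's 10% and the table's 20%.

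**Step 4: can <10%/<10% be met at a 35% target?** The Stage 1 stop alone misses an active drug with probability P(X1 = 0 | 0.35) = 0.65⁵ = 11.6%. No final cut-off can then bring the FNR below 10%.

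**Step 5: how often do the two rules disagree?** They differ when the total is exactly 2 of 9 with at least one Stage 1 responder:

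P = P(X1 = 1)·P(X2 = 1) + P(X1 = 2)·P(X2 = 0)

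- p = 0.35: 0.1201 + 0.0601 = 0.1802.
- p = 0.10: 0.0957 + 0.0478 = 0.1435.

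If 2 of 5 is credited at Stage 1, only the first term disagrees: 12.0% and 9.6%.

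**The case against.** The strongest reply is that little depends on this boundary. The SAP's Study Design section uses the design only as a guide ("Although a 2-stage (Fleming) design will be used to guide assessment of preliminary anti-tumor" activity), no hypothesis is formally tested, and no cohort stops for efficacy. Continuing a cohort is a sponsor and medical monitor decision on the accruing evidence as a whole. A reader who follows the citation finds the cohort-specific values directly below. All of this stands and limits the consequence. It does not reconcile the sentence with its source.

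Second, futility stopping is described as an option, and up to 9 subjects may be enrolled per cohort. If all 9 are enrolled without a futility stop, the table rule gives FPR 22.5% and FNR 12.1%, the text rule gives 5.3% and 33.7%, and exactly 2 of 9 occurs with probability 21.6% (true ORR 35%) or 17.2% (10%). Step 4's impossibility result is then also lost for FNR alone: passing at 1 or more of 9 gives FNR 0.65⁹ = 2.1%, but FPR 1 − 0.9⁹ = 61%. No cut-off meets both targets, so the conclusion survives.

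Third, the text rule on its own does meet the FPR half of its target (5.1% or 9.9%). The failure is in the FNR, so the joint <10%/<10% statement is what is wrong.

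Fourth, the text might be the intended rule, since the SAP allows the assumed rates to be updated. That allowance covers later changes to assumptions. It does not explain a sentence that disagrees with a table carried over unchanged from the protocol.

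**Conclusion.** The concern holds. For non-GC-DLBCL and CRPC, the SAP text and the table it cites give opposite verdicts on 2 of 9. The text's joint error target is not met under either cut-off.

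The table is the sound version: its error rates reproduce, both documents carry it, and no final cut-off with 5 then 9 subjects meets <10%/<10% at a 35% target. The text reads as the 50%-target rule written as if it covered all five cohorts.

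The disagreement has probability 18.0% per affected cohort at a true ORR of 35% and 14.3% at 10%, assuming futility at 0 of 5 is applied and no Stage 1 credit is given. Across the variants in the working and objection the range is 12.0% to 21.6% at 35% and 9.6% to 17.2% at 10%. The effect is confined to the reading of the efficacy signal; the planned ORR estimates and Clopper-Pearson intervals do not change.

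**What to change.** Make two sentences in SAP Section 5.2 cohort-specific:

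- **Final rule:** the target ORR is not supported if 2 or fewer of 9 respond in NMC, DHL or TNBC, or if 1 or fewer of 9 respond in non-GC-DLBCL or CRPC, per Table 5.2-1.
- **Error targets:** FPR/FNR of 10%/10% for NMC, DHL and TNBC, and 20%/20% for non-GC-DLBCL and CRPC.

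The cost is two sentences, with no change to the table, sample size, design or planned analyses. If the sponsor does intend <10%/<10% for every cohort, rewording is not enough: the table and the size of the two 35% cohorts would have to change. For scale, an exact single-stage design for 35% vs 10% at 10%/10% needs 18 subjects, with success at 4 or more responders.

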## **6 STUDY PERIODS, TREATMENT REGIMENS AND POPULATIONS FOR ANALYSES**

### **6.1 Study Periods**

This study consists of four periods: Screening (up to 28 days for Part 1 and up to 40 days for Part 2), Treatment, Clinical Follow-up (30 days), and Survival Follow-up.

#### **6.1.1 Baseline Period**

- The screening period is up to 28 days for Part 1 and up to 40 days for Part 2 and is immediately prior to the first study drug administration. The screening period begins by establishing the participant's initial eligibility and signing of the informed consent form (ICF).
- Baseline evaluations or events will be defined as evaluations or events that occur before the date and time of the first dose of study treatment unless otherwise specified.

#### **6.1.2 Post-Baseline Period**

- The On-treatment period starts at the time of the first dose of study medication and ends when the decision to discontinue a subject from study therapy is made.
- The clinical follow-up period begins when the decision to discontinue a subject from study therapy is made, and for subjects treated with BMS-986158 in monotherapy extends until 30 days after a subject discontinues.
- The survival follow-up period begins 30 days after a subject discontinues from study therapy, and ends 2 years after the first dose of study drug unless continuing on study treatment for more than 2 years, or 6 months after his/her last treatment date, whichever occurs later.

### **6.2 Treatment Regimens**

The treatment group “as assigned” will be retrieved from the IRT system, if applicable. The treatment group “as treated” will be the same as the arm as assigned by IRT. However, if a participant received an incorrect treatment for the entire period of treatment, the participant's treatment group will be defined as the incorrect treatment the participant actually received.

Statistical analysis and reporting will be performed based on the treatment regimen assigned to subjects at the time of study therapy initiation unless otherwise specified. For Part 1 Schedule A the 5 days on / 2 days off regimen will be considered as the assigned treatment, even though subjects are expected to receive a single dose in Cycle 1 (i.e., the first week of therapy), with the exception of the PK analysis where the single dose PK will be presented separately for the Cycle 1 Week 1 schedule. The regimens administered in Part 1 via Schedules B and C will be handled equivalently. Part 2 Schedule A (QD dosing for 5 consecutive days of each week, followed by a 2-day rest period, on a 28-day cycle) has been chosen for expansion. The initial dose level of BMS-986158 selected for Part 2 is 4.5 mg with a loading period of 2 weeks (10 doses or half a cycle) with subsequent dose level of 3.75 mg for the duration of study treatment for each subject.

### 6.3 Populations for Analyses

- All Enrolled: All participants who provided an informed consent form.
- All Treated: All participants who received at least one dose of any study medication.
- Pharmacokinetic: All participants who received at least one dose of BMS-986158 and have available serum or plasma concentration data for the corresponding analyte
- Pharmacokinetic evaluable: Subset of Pharmacokinetic population with adequate PK Profiles who have at least 1 valid PK parameter. Pharmacokinetic summaries and statistical analyses will be based on this dataset.

- ECG Evaluable: all treated participants who had a baseline ECG and at least one on study ECG.
- Response-evaluable: all treated participants with measurable disease at baseline and at least one of the following: 1) at least one post-baseline tumor assessment, 2) clinical progression, or 3) death.

All subjects who receive study medication will be included in the safety population.

## 7 STATISTICAL ANALYSES

All analyses will be performed using the SAS System Version 9.2 or later. Some figures will be generated using S-Plus or R.

### 7.1 General Methods

Continuous variables will be summarized using descriptive statistics including mean, standard deviation (SD), standard errors of the mean (SEM), median, minimum, and maximum. PK endpoints will also report geometric means, standard deviations, and standard errors of the mean. Categorical variables will be summarized using frequencies and percentages. Percentages will be rounded to one decimal precision and may sum to more or less than 100.0. Percentages less than 0.1 will be indicated as '< 0.1'. For summaries, tumor types that have less than 5 participants may be grouped together with "Other".

Time-to-event (TTE) endpoints will be evaluated using Kaplan-Meier (K-M) methods. Regimen describes BMS-986158 monotherapy

### Study Conduct

#### 7.2.1 Study Information

- **Listing:**
- Batch number listing for all treated subjects will be provided.

#### 7.2.2 Accrual

The following will be presented using the All Enrolled population.

#### **Summary:**

- Number (%) of participants accrued by country and investigational site: include country, site number, number of subjects enrolled, and number of participants treated
- **Listing:**

- Participants accrued by country and investigational site

### **7.2.3 Relevant Protocol Deviations**

Non-programmable relevant eligibility and on-treatment protocol deviations, as well as significant (both programmable and non-programmable) deviations will be reported through ClinSIGHT listings. The following programmable deviations from inclusion and exclusion criteria will be considered as relevant protocol deviations and a listing will be provided, based on data availability.

#### **At entrance:**

- Participants with baseline ECOG performance status > 1
- Participants who used strong inhibitors of CYP3A4 or P-gp within 2 weeks or strong inducers of CYP3A4 or P-gp within 2 weeks.
- Participants with inadequate hepatic function:
  - Aspartate aminotransferase (AST) > 3x ULN
  - Alanine aminotransferase (ALT) > 3x ULN
  - Total bilirubin > 1.5 x ULN (except known Gilbert's syndrome)
- Participants with inadequate bone marrow function:
  - Absolute neutrophil count (ANC) < 1,500 cells/mm^3;
  - Platelet count < 100,000 cells/mm^3;
  - Hemoglobin < 8 g/dL
- Participants with abnormal blood coagulation parameters:
  - PT such that international normalized ratio (INR) is > 1.5 (or > 3, if a subject is on a stable dose of therapeutic warfarin) and a PTT > 1.2x upper limit of normal (ULN).
- Participants with positive blood screen for hepatitis C antibody or hepatitis B surface antigen

#### **On-Study:**

- Participants receiving concurrent anti-cancer therapy (defined as chemotherapy, hormonal immunotherapy, non palliative radiation therapy, standard or investigational agents for treatment of NSCLC).
- Participants who received the wrong dose level

## **7.3 Study Population**

### **7.3.1 Participant Disposition**

Status of participants at the end of pre-treatment period will be summarized and listed by including all enrolled participants. Status of participants at the end of treatment period will be summarized by treatment and overall, based on All Treated population. In addition, status of participants at the end of each study period will be summarized as appropriate. A listing will be provided for those participants who were treated and reason for discontinuation of treatment or not being followed will be described.

### **7.3.2 Demographics and Other Baseline Characteristics**

#### **Summary:**

Descriptive statistics will be summarized the following baseline characteristics for all treated subjects by treatment and overall, and may also be presented by tumor type.

- Age (in years) ; age category (<65, 65 - 84, ≥85),
- Sex at Birth
- Race
- Ethnicity (if applicable)
- Country
- Physical characteristics
  - Height
  - Weight
- ECOG PS

#### **Listing:**

- All relevant data, generally the variables listed above by treatment.
- General medical history

### **7.3.3 Prior Anti-Cancer Therapy**

#### **Summary:**

Summary statistics will be provided by treatment and overall for each tumor type for:

- Prior systemic cancer therapy
  - Number of prior therapies and lines of therapy
- Prior surgery
  - Number of subjects with prior surgery
- Prior radiotherapy therapy
  - Number of subjects with prior radiotherapy

#### **Listing:**

- Prior surgery and radiotherapy
- Prior systemic cancer therapy
  - Best response to therapy

### **7.3.4 Baseline Disease Diagnosis**

#### **Summary:**

Summary statistics will be provided by treatment and overall and also separately by tumor type.

- Baseline Disease Diagnosis, and disease characteristics (e.g. stage)

**Listing:**

- Baseline Disease Diagnosis

**7.4 Extent of Exposure**

Subjects' extent of BMS-986158 exposure will be characterized using the number of subjects exposed, and the duration of exposure by the BMS-986158 dose levels assigned. Analyses in this section will be performed using the All Treated population.

Three BMS-986158 dosing schedules in Part 1 will be described: monotherapy single weekly dosing followed by 1) five consecutive daily doses per week, 2) 14 consecutive daily doses followed by 7 days of non-dosing per three week period, 3) 7 consecutive daily doses followed by 14 days of non-dosing per three week period. BMS-986158 schedule A will be administered in Part 2 initial expansion as BMS-986158 Monotherapy.

Extent of exposure to BMS-986158 will be characterized by the number of oral dosings, duration of therapy, cumulative exposure, and absolute and relative dose intensity.

